3.5.6 Drug levels and pharmacokinetic assessments

No pharmacokinetic assessments are planned.

4 Protocol amendments, other changes in study conduct

4.1 Protocol amendments

Any changes to the protocol will be made in the form of an amendment

4.2 Other changes in study conduct

Changes in study conduct are not permitted without an amendment to the protocol. Any unforeseen deviations in study conduct will be recorded in the clinical study report.

5 Data management

5.1 Data collection

Selected Visit 1 information will be collected using IVRS. Starting at Visit 2 investigators must enter the information required by the protocol onto the Novartis Case Report Forms (CRFs) that are printed on 3-part, no carbon required (NCR) paper. Field monitors will review the IVRS printouts and CRFs for completeness and accuracy, and instruct site personnel to make any required corrections or additions. The CRFs are forwarded to the Novartis Medical Documents Reception Center or designee by field monitors or by the investigational site, one copy being retained at the investigational site. Once the CRFs are received by Novartis or designee, their receipt is recorded, the original copy is placed in Central Files and the NCR copy is forwarded to the responsible medical data management staff for processing. If CRFs are sent directly to Novartis or designee by investigational sites, they are reviewed prior to data entry.

5.2 Database management and quality control

Visit 1 information will be transferred from IVRS into the trial database. Data items from the CRFs are entered into the study database using double data entry with electronic verification.

Subsequently, the information entered into the database is systematically checked by Data Management staff, using error messages printed from validation programs and database listings. Obvious errors will be corrected by Novartis personnel or designee. Other errors or omissions will be entered on Data Query Forms, which will be returned to the investigational site for resolution. A copy of the signed Data Query Form is to be kept with the CRFs, and once the original is received at Novartis or designee the resolutions will be entered into the database. Quality control audits of all key safety and efficacy data in the database will be made after entering data from each visit.

Concomitant medications entered into the database will be coded using a WHO Drug Reference List. Coexistent diseases and adverse events will be coded using MEDDRA.

Laboratory samples will be processed through a central laboratory, and the results will be sent electronically to Novartis or designee.

When the database has been declared to be complete and accurate, the database will be locked and unblinded. Any changes to the database after that time can only be made by joint written agreement between the Clinical Trial Leader, the Trial Statistician and the Data Manager.

6 Statistical methods

6.1 Statistical methods

The primary efficacy parameters of this study are time to progression to diabetes and time to first occurrence of an extended and time to first occurrence of a core CV endpoint. These three endpoints will be tested in parallel using a closed testing procedure for each drug. It is thus possible to achieve statistical significance for any one endpoint independent of the others (under sensible assumptions; see below).

The closed testing procedure proposed combines weighted Bonferroni and weighted trimmed Simes (Hochberg) tests. Progression to diabetes and the cardiovascular endpoints are always tested asymmetrically, with a 1:4 weight allocation, respectively. The two cardiovascular endpoints are equally weighted as (i) they are equally important, and (ii) the impact of the treatment effect differences between extended and core CV endpoints (assumed to be larger for the core CV endpoint which in turn is less frequent than the extended CV endpoint) on the power of statistical tests is unclear. The trimmed Simes (Hochberg) test is applied to the pairwise intersection hypotheses and the intersection of the cardiovascular endpoints hypotheses in the 3-way (global) intersection hypothesis. In case of independent or positively correlated test statistics, the Simes (Hochberg) test for two hypotheses allows rejection a) if one of the tests is “significant” at its individually allocated level (e.g. nominal alpha levels of 0.01 and 0.04), or b) if both tests are “significant” at the sum of the individual levels (i.e., 0.05 in above example).

In this study it can be safely assumed that the test statistics related to the extended and core CV endpoints are non-negatively correlated. A negative correlation between the test statistics relative to the progression to diabetes and cardiovascular endpoints cannot be ruled out, however. On the other hand, relevant (particularly statistically significant) treatment differences for both the diabetes and CV endpoints but in favor of different treatments will have a rather low likelihood. Otherwise this study would certainly not have been done and use of the trimmed Simes test would not be recommendable.

When there is possibly a negative correlation between the (one-sided) test statistics a trimmed version of the (asymmetric) Simes test controls the overall type I error α as follows: reject the intersection hypothesis $H_A \cap H_B$ if (a) $p_A < \alpha$ & $p_B < \alpha$, or (b) $p_A < \alpha_A$ & $\underline{p_B < 1 - \alpha_B}$, or (c) $\underline{p_A < 1 - \alpha_A}$ & $p_B < \alpha_B$, where $\alpha = \alpha_A + \alpha_B$, and p_A and p_B are one-sided p-values related to the individual hypotheses H_A and H_B . The underlined conditions are additional requirements and can be considered rather mild as the rejection of an individual hypothesis relative to one endpoint would fail only if there were a (statistically significantly) strong effect of the other endpoint in the opposite direction. As argued above, the odds of such a finding in this trial are very low and also the overall conclusions from this trial would be inconclusive anyway.

The closed testing strategy with seven intersection hypotheses for the three primary endpoints is summarized in Table 6. As described it is only valid if no interim analysis was performed. Its modification to account for the interim efficacy analysis performed in December 2005 is detailed in Section 6.1.7.

Table 6 Closed testing strategy for the three primary endpoints

Endpoint	In order for the endpoint to be statistically significant, the following intersection hypotheses must be rejected	
Progression to diabetes	$PD \cap CE \cap CC$; $PD \cap CE$; $PD \cap CC$; $PD \cap \square \cap \square$	
Extended CV endpoint	$PD \cap CE \cap CC$; $PD \cap CE$; $CE \cap CC$; CE	
Core CV endpoint	$PD \cap CE \cap CC$; $PD \cap CC$; $CE \cap CC$; CC	
Intersection hypothesis	One-sided tests applied (weights in parentheses)	Requirement for rejection (nominal p-values (*))
$PD \cap CE \cap CC$	Weighted Bonferroni for PD (0.2) and the intersection hypothesis $CE \cap CC$ (0.8); unweighted trimmed Simes for CE (0.5) and CC (0.5)	$p_{PD} < .005$ or $p_{CE} < .01$ & $p_{CC} < .99$ or $p_{CC} < .01$ & $p_{CE} < .99$ or $p_{CE} < .02$ & $p_{CC} < .02$
$PD \cap CE$	Weighted trimmed Simes for PD (0.2) and CE (0.8)	$p_{PD} < .005$ & $p_{CE} < .98$ or $p_{CE} < .02$ & $p_{PD} < .995$ or $p_{PD} < .025$ & $p_{CE} < .025$
$PD \cap CC$	Weighted trimmed Simes for PD (0.2) and CC (0.8)	$p_{PD} < .005$ & $p_{CC} < .98$ or $p_{CC} < .02$ & $p_{PD} < .995$ or $p_{PD} < .025$ & $p_{CC} < .025$
$CE \cap CC$	Unweighted trimmed Simes for CE (0.5) and CC (0.5)	$p_{CE} < .0125$ & $p_{CC} < .9875$ or $p_{CC} < .0125$ & $p_{CE} < .9875$ or $p_{CE} < .025$ & $p_{CC} < .025$
PD		$p_{PD} < .025$
CE		$p_{CE} < .025$
CC		$p_{CC} < .025$
Characteristics of procedure (summary)	
 - All three endpoints are primary endpoints - PD on the one hand and CE / CC on the other hand are always tested using a 1:4 weight allocation - CE and CC are weighted equally - tests are one-sided - Simes procedure has been modified (through trimming) in order to preserve the type I error under any correlation between the test statistics 	
Notation:	Null hypothesis associated with	
PD	Progression to diabetes	
CE	Extended CV endpoint	
CC	Core CV endpoint	

(*) To account for the interim efficacy analysis already performed, the (one-sided) alpha level of this testing procedure at the final analysis will be less than 0.025; this is detailed in Section 6.1.7

The following example may help to understand the closed testing procedure. In order to claim that there is a positive effect on the core CV endpoint, say, all four intersection hypotheses involving this endpoint must be rejected, namely $H_{CC} \cap H_{CE} \cap H_{PD}$, $H_{CC} \cap H_{CE}$, $H_{CC} \cap H_{PD}$,

and H_{CC} . Now let's suppose that the p-values p_{CC} , p_{CE} and p_{PD} relative to H_{CC} , H_{CE} and H_{PD} , respectively, are 0.0096, 0.0188, and 0.1583, say. From the right-hand column in above table we see that (1) $H_{CC} \cap H_{CE} \cap H_{PD}$ can be rejected as the condition $p_{CC} < .01$ & $p_{CE} < .99$ is fulfilled, (2) $H_{CC} \cap H_{CE}$ can be rejected as the condition $p_{CC} < .0125$ & $p_{CE} < .9875$ is fulfilled, (3) $H_{CC} \cap H_{PD}$ can be rejected as the condition $p_{CC} < .02$ & $p_{PD} < .995$ is fulfilled, and (4) H_{CC} can be rejected as the condition $p_{CC} < .025$ holds. One can therefore conclude that there is a statistically significant between-treatment group difference as to the core CV endpoint. With above p-values the very same statement holds for the extended CV endpoint, but not for progression to diabetes.

Time to progression to diabetes will be analyzed using a discrete time proportional odds model. Time to first cardiovascular event (in days) for both the extended and core CV endpoints will be analyzed using a logrank statistic. The trial will be stopped and the final analysis performed when 1374 patients have had an Adjudication Committee-confirmed extended CV endpoint.

Tests will be performed separately for both valsartan and nateglinide, unless stated otherwise. The primary tests will be for the main effect of an experimental treatment (i.e. nateglinide or valsartan), stratified for the other treatment (i.e. valsartan or nateglinide) and for CVD at baseline.

Formal efficacy interim analyses were foreseen at two time-points during the trial. A first efficacy interim analysis was performed in December 2005; the second one will be dropped (see Sections 3.1 and 6.1.7).

Additional exploratory efficacy endpoints will also be analyzed.

Demographic and baseline characteristics, exposure to study medication, concomitant medication and safety information will be presented primarily in descriptive tables using summary statistics. Summaries will be by treatment groups (i.e. four groups included).

Baseline is either the measurement at Visit 2, or the last measurement prior to Visit 2 if no Visit 2 value is available. HbA1c will also be measured at baseline (Visit 2).

6.1.1 Populations

The primary efficacy analysis will be based on the intent to treat (ITT) population. This population will consist of all randomized patients. Patients will be classified into the treatment groups they were assigned to by the IVR system.

Analyses will also be done for the per protocol (PP) population. This population will consist of all patients in the ITT population without major deviations from the protocol. "Major deviations" will be defined under blinded conditions. The safety analyzable (or safety) population will contain all randomized patients who had at least one post-baseline safety measurement.

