3.3.3 Interruption of treatment

All randomized patients, including patients who have achieved a glycemic and/or non-fatal cardiovascular endpoint, should remain on trial treatment (Treatment A, Treatment B) until death or trial end. The following conditions may be reasons to interrupt the trial treatment:

- the patient decides it is in his/her best interest (i.e., patient unwilling to take medication)
- the investigator considers it advisable or in the patient's best interest
- adverse experience(s)
- abnormal laboratory value(s)

Each treatment (Treatment A, Treatment B) can be interrupted individually. The reason for treatment interruption will be collected. If study treatment is interrupted, every effort must be made to reinstate treatment as soon as possible and medically acceptable. Reinstatement of trial treatment is not subject to a time limit and may occur after days, weeks, months, or even years. The number of attempts to re-initiate is also not limited. When treatment is re-initiated, it is not necessary to begin with the lowest dose level. At the investigator's discretion, re-initiation of trial treatment may start with the last dose level. Patients with a treatment interruption should continue the protocol visit schedule and comply with all study procedures, except treatment dispense.

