3.4.5 Treatment assignment

Subject Number

At Visit 1, each individual will receive a unique subject identification number. The subject identification number is composed of two parts. The first part is the center number, assigned to the center by the sponsor, and the last part is the subject number, which is sequentially assigned by the center to patients as they enter the study. For example, the third patient enrolled in Center 35 would be identified as 0035-0003. Once assigned, subject numbers must not be reused.

Subjects may be re-screened only one time and after approval by Novartis. Re-screened subjects must provide a new informed consent and will be assigned a new subject number.

Randomization

At randomization (Visit 2, Month 0), eligible subjects will be assigned to one (Treatment A and Treatment B) of the four treatment groups (ratio 1:1:1:1) via an Interactive Voice Response System (IVRS). A patient will be considered randomized when the subject number is entered into the IVR system and the phone call is completed.

At Visit 2 (randomization), 3, 4, 6 and every visit thereafter, trial treatment will be assigned via an IVRS.

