3.5.4 Safety assessments

Safety assessments will consist of monitoring and recording all adverse events and serious adverse events, the regular monitoring of hematology, blood chemistry (including liver enzymes) and urine values, regular measurement of vital signs and the performance of physical examinations and ECG.

Adverse events

Information about all adverse events, whether volunteered by the subject, discovered by investigator questioning, or detected through physical examination, laboratory test or other means, will be collected and recorded in the patient's source documents and CRF and followed as appropriate.

An adverse event is any undesirable sign, symptom or medical condition occurring after starting study drug(s) (or therapy) even if the event is not considered to be related to study drug (or therapy). Study drug (or therapy) includes the drug (or therapy) under evaluation, and any reference or placebo drug (or therapy) given during any phase of the trial.

Medical conditions/diseases present before starting study treatment are only considered adverse events if they worsen after starting study treatment. Adverse events occurring before starting study treatment but after signing the informed consent form are recorded on the Medical History/Current Medical Conditions Case Report Form. Abnormal laboratory values or test results constitute adverse events only if they induce clinical signs or symptoms or require therapy, and are recorded on the Adverse Events Case Report Form under the signs, symptoms or diagnosis associated with them.

As far as possible, each adverse event will also be described by:

1. its duration (start and end dates),
2. the severity grade (mild, moderate, severe)
3. its relationship to the study drug (suspected / not suspected),
4. the action(s) taken and, as relevant, the outcome.

Examples of the severity grade, relationship to study drug and actions taken, as presented in the case report form are provided in Section 8.1.3, Instructions for completing Adverse Event Case Report Forms.

Pre-defined safety and tolerability parameters

The following pre-defined safety and tolerability conditions are known side effects of valsartan and nateglinide and will be recorded on the CRF.

Valsartan

Hypotension

Hypotension is defined as the mean of 2 sitting diastolic or systolic blood pressure measurements of < 60 mm Hg or < 100 mm Hg, respectively.

Orthostatic hypotension

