6.1.6 Safety evaluation

The assessment of safety will be based mainly on the frequency of all adverse events and on the number of laboratory values that fall outside of pre-determined ranges. Other safety data (e.g. electrocardiogram, vital signs, special tests) will be considered as appropriate.

Adverse events will be summarized by presenting, for each treatment group, the number and percentage of patients having any adverse event, having an adverse event in each body system and having each individual adverse event. Any other information collected (e.g. severity or relatedness to study medication) will be listed as appropriate.

For the subset of patients at prospectively defined study centers who will be dispensed glucometers, the number and percentage with confirmed hypoglycemic events (plasma glucose < 3.3 mmol/l) will be presented. The number and percentage of patients with any events suggestive of hypoglycemia will also be presented for this subset, in order to be able to put the number of confirmed vs. suggestive events into a perspective. Patients who were dispensed glucometers at the investigator's discretion (i.e. not from the pre-defined centers) will not be shown in this summary.

Laboratory data will be summarized by presenting shift tables using extended normal ranges (baseline to most extreme post-baseline value), by presenting summary statistics of raw data and change from baseline values (means, medians, standard deviations, ranges) and by the flagging of notable values in data listings.

Data from other tests (e.g. electrocardiogram or vital signs) will be listed, notable values will be flagged, and any other information collected will be listed as appropriate.

Unless otherwise indicated, the safety population will be used for the safety analyses.

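### The safety population is defined by a post-baseline measurement and not by exposure, so its denominator does not match the protocol's adverse-event definition; the effect is probably small

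*Protocol*

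**What the plan says.** Section 6.1.1 of the protocol states that the safety population "will contain all randomized patients who had at least one post-baseline safety measurement". Section 6.1.6 makes this the default set: "Unless otherwise indicated, the safety population will be used for the safety analyses". The main safety table gives, by treatment group, "the number and percentage of patients having any adverse event".

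Section 3.5.4 ties the numerator to exposure. Its definition begins "An adverse event is any undesirable sign, symptom or medical condition occurring after starting study drug(s) (or therapy", and goes on to say that the event need not be related to the drug. Earlier events go elsewhere: "Adverse events occurring before starting study treatment but after signing the informed consent form are recorded on the Medical History", on a separate form.

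Randomization is not tied to a first dose. Section 3.4.5 states: "A patient will be considered randomized when the subject number is entered into the IVR system and the phone call is completed". Patients off treatment stay under observation. Section 3.3.3 states: "Patients with a treatment interruption should continue the protocol visit schedule and comply with all study procedures, except treatment dispense". Section 3.5.2 allows discontinuation from the study before trial end only for death.

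**The concern.** The numerator and the denominator of the adverse-event percentages follow different rules: the numerator requires exposure, the denominator requires a measurement. This can go wrong in two ways.

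- **Never-dosed patients are counted.** A patient who is randomized, takes nothing and attends one visit is in the safety population. Under section 3.5.4, nothing that happens to that patient is an adverse event. Absolute rates and risk differences are pulled towards zero.
- **Dosed patients can be left out.** The first scheduled visit after randomization is Visit 3, at week 2, with a tolerance of one week (section 3.5.1). A patient who takes the first doses and is never assessed again has no post-baseline measurement. For a patient who dies in that window, the wording does not settle the matter.

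What is at stake is how faithfully absolute harm is described, above all just after first exposure. The primary efficacy results are not affected.

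**Working it through.** The protocol gives no never-dosed count, no all-cause mortality rate and no size for the safety population, so it has no figure on this point to reproduce. The arm size does agree: 9152 / 4 = 2288, as in section 3.3.1.

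**Step 1. The rules side by side**

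| Patient | In the safety population (6.1.1)? | Can have an adverse event (3.5.4)? |
|---|---|---|
| Dosed, seen later | Yes | Yes |
| Never dosed, seen later | Yes | No (serious events apart, see objection) |
| Dosed, no later safety measurement | No | Yes |
| Dosed, dies before Visit 3 | Undetermined | Yes |

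The second and third rows are the mismatch. The fourth is undetermined because safety measurement is not defined.

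**Step 2. Dilution by never-dosed patients**

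Let f be the share of the safety population that was never dosed (an assumption). Then observed rate = true rate × (1 − f). With 2288 patients in an arm and a true rate of 10%:

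| Assumed f | Never-dosed patients per arm | Observed rate |
|---|---|---|
| 0.1% | 2 | 9.99% |
| 1% | 23 | 9.90% |
| 2% | 46 | 9.80% |
| 5% | 114 | 9.50% |

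A true difference of 5 points (10% against 5%) becomes 4.95 points at f = 1% and 4.75 points at f = 5% if f is the same in both groups. The rate ratio then stays at 2, because (1 − f) cancels.

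**Step 3. Dosed patients without a later measurement**

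Section 6.2 assumes 30% treatment discontinuation over five years and expects 75% of those patients to be followed for events. With a constant hazard, −ln(0.70)/5 = 0.0713 per year. Expected discontinuers among 9152 are 9152 × (1 − exp(−0.0713 × w/52.18)), which is about 25 at w = 2 weeks and 37 at w = 3 weeks. A quarter of these not followed gives about 6 to 9 patients, or 0.07% to 0.10% of those randomized. This is only a rough guide: the 25% in section 6.2 also covers deaths without a primary endpoint and unreported events.

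**Step 4. Deaths before Visit 3**

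At an assumed all-cause mortality m, deaths in 14 days = 9152 × m × 14/365.25. This gives 1.8, 3.5 and 7.0 for m = 0.5%, 1% and 2% per year, so about 2 to 7 over all four arms.

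As a cross-check, section 6.2 assumes a placebo rate of 4% per year for the extended cardiovascular endpoint. With hazard −ln(0.96) = 0.0408 per year, that gives about 14 first events by week 2 and 21 by week 3 among 9152. If 10% to 30% of these were fatal (an assumption), about 1 to 6 patients would have died of a cardiovascular cause.

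**The case against.** The case against giving this much weight is strong, and most of it stands.

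- **Early deaths.** A reader might infer that patients who die before Visit 3 drop out of every safety table, or out of the trial's results. The documents do not support that. Section 3.5.4 includes the recording of serious adverse events among the safety assessments, and a death must be reported whenever it occurs, so a recorded fatal event may itself be the qualifying measurement. Cardiovascular death belongs to both cardiovascular primary endpoints, and time to all-cause death is an exploratory analysis (6.1.5.2). These are analysed in all randomized patients (6.1.5.1), and section 3.5.2 requires vital status to be followed. What remains is an undefined term.
- **Every rate diluted.** A reader might also infer that all safety percentages are affected. That is too broad. Serious adverse events are reportable from informed consent (8.1.1.1), so a never-dosed patient can contribute one. Section 3.5.4 defines hypotension by blood-pressure values alone. Confirmed hypoglycemia is summarised in patients at predefined glucometer centers (6.1.6).
- **Patients lost early.** The definition sets no time limit, so a patient who misses Visit 3 and is seen later is included. Those left out have no safety measurement at all. Counting them adds to the denominator without ascertainment, which also lowers percentages slightly.
- **Imbalance between arms.** Selection on a measurement taken after randomization could differ by arm, but nothing in the documents shows that it would. Treatment is double-blind with matching placebo, and drug is dispensed at the randomization visit itself, so a large never-dosed group is unlikely. Safety is presented mainly descriptively (6.1), so no formal safety test depends on this.

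None of this removes the mismatch. The protocol states the rule itself, so this is not a detail left to the analysis plan.

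**Conclusion.** The point holds as a minor one. The safety denominator is selected by a measurement, while the adverse-event definition requires that drug was started. Never-dosed attendees therefore count in the denominator of the non-serious adverse-event percentages without being able to enter the numerator, and dosed patients with no later safety measurement are excluded. The status of a patient who dies before Visit 3 is not settled by the text.

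The size is probably small. A true 10% rate is reported as 9.90% if 1% were never dosed and 9.50% if 5% were. On the assumptions used above, the early exclusions in question number about 6 to 9 patients lost and 2 to 7 deaths among 9152. The never-dosed share and the mortality rate are assumptions, and the count of patients lost rests on the planning rates of section 6.2. The documents do not show a material distortion of the safety conclusions, a bias between arms, or a loss of early deaths from the trial.

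**What to change.** In section 6.1.1, define the safety population as all randomized patients who took at least one dose of Treatment A or Treatment B, with no requirement for a post-baseline measurement. This puts numerator and denominator on the same rule. It also settles early deaths after dosing without the need to define safety measurement.

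The change is one sentence and does not touch trial conduct, alpha or the efficacy analyses. The data are largely to hand: dispensing is captured through the voice response system and interruptions on the case report form (3.4.8), and duration on treatment is already to be summarised (6.1.3). Since dispensing is not intake, the definition should also say how a patient with drug dispensed but no information on intake is classified.

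There are two downsides. Laboratory and vital-sign tables will show a smaller n than the population size. A few dosed patients with no follow-up will count in the denominators without adverse-event ascertainment; their number should be reported by arm.
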